6.4.2.1.3. Exploratory Analysis

Exploratory analyses using the same methods described above will be used to assess for immune response of mRNA-1273.529 compared to mRNA-1273 booster administered against other variant strains (e.g., Alpha, Beta, etc.) after study vaccination. Specifically, for each antibody of interest, the GMT, GMFR and SRR and corresponding 95% CI will be calculated at the time point in which immune response against other variant strains are assessed. Comparisons between booster regimens will be explored by calculating the GMR and differences in SRRs with corresponding 95% CIs, as outlined above.

Exploratory analysis will be performed of the Month 12 immune response using the same methods described above of mRNA-1273.529 compared to mRNA-1273 booster against the B.1.1.529 strain, prototype strain and other variant strains overall and by the Phase B subgroup stated in [Section 6.1](#).

The same ANCOVA model described above may be used for exploratory analyses to assess for immune response of mRNA-1273.529 compared to mRNA-1273 booster administered as a 4th dose against both the B.1.1.529 and the prototype strain at Day 29, using a 95% CI for GLSM and GMR.

Similar analyses will be used to assess for immune response of mRNA-1273.529 compared to mRNA-1273 booster administered against the BA.4/BA.5 variant strains, conducted in the random sample of 200 participants. The exception will be the sensitivity analysis of SRR performed in the PPSI using the stratified Miettinen-Nurminen method, where both SARS-CoV-2 status (positive, negative, and unknown) and age group (≥ 16 to < 65 , and ≥ 65 years) will be included as strata.

6.4.2.2. Part 2 (mRNA-1273.214 and mRNA-1273)

6.4.2.2.1. Primary Analyses

For the primary objective on immune response for the second booster (4th dose) of mRNA-1273.214, there are six primary hypotheses to be tested (see [Section 4.2](#)). Serum neutralizing antibody will be used as the basis to assess non-inferiority and superiority in immune response. The primary analysis set for immunogenicity objectives will be based on PPSI-Neg.

Day 29 (alpha=0.01, two-sided)

The same ANCOVA model described for Part 1 will be used to assess the difference in immune response between mRNA-1273.214 and mRNA-1273 in the subgroup of participants who received the 4th dose. To test the first primary hypothesis as to if a single booster dose of mRNA-1273.214 is non-inferior to mRNA-1273 based on GMR against the B.1.1.529 strain at Day 29 an ANCOVA will be performed with antibody titers at Day 29 post-booster against the B.1.1.529 as the dependent variable, and a group variable (mRNA-1273.214 and mRNA-1273) as the fixed effect, adjusting for age groups (≥ 16 to < 65 , ≥ 65 years), most recent COVID-19 vaccination type (mRNA or viral vector) and pre-booster antibody titer level, if applicable. The GMT will be estimated by the GLSM from the model and corresponding 99% CIs will be provided for each group. The GMR for mRNA-1273.214 with respect to mRNA-1273 will be estimated by the ratio of GLSM from the model and the corresponding 99% CIs will be provided. The non-inferiority of immune response of mRNA-1273.214 as compared to mRNA-1273 against the B.1.1.529 strain for mRNA-1273.214 at Day 29 will be considered demonstrated if the lower bound of the corresponding 99% CI of the GMR is ≥ 0.67 based on a non-inferiority margin of 1.5.

The same ANCOVA model will be performed to assess the non-inferiority of immune response against the prototype strain in the subgroup of participants who received mRNA-

1273.214 and mRNA-1273 as the 4th dose (second primary hypothesis). The non-inferiority is demonstrated if the lower bound of the corresponding 99% CI of the GMR is ≥ 0.67 based on a non-inferiority margin of 1.5.

Once non-inferiority against B.1.1.529 and prototype strains is demonstrated, superiority of mRNA-1273.214 as compared to mRNA-1273 against B.1.1.529 will be tested (at Day 29). If the lower bound of the 99% CI of the GMR is > 1 , superiority is demonstrated (third primary hypothesis).

Month 3 (alpha=0.04, two-sided)

The same ANCOVA model will be used to assess immune response of mRNA-1273.214 against the B.1.1.529 strain at Month 3 (fourth and six primary hypotheses). The 96% CI for GMR will be used to assess the between group difference in immune response against the B.1.1.529 strain for non-inferiority and superiority. The same ANCOVA model, and the lower bound of the corresponding 96% CI that is ≥ 0.67 based on a non-inferiority margin of 1.5 will be used to demonstrate the non-inferiority for the immune response against the prototype virus strain at Month 3 (fifth primary hypothesis).

Part 2 of this study is considered to have met its primary objective if non-inferiority of mRNA-1273.214 against the B.1.1.529 strain, non-inferiority of mRNA-1273.214 against the prototype strain, and superiority of mRNA-1273.214 against the B.1.1.529 strain are demonstrated as compared to mRNA-1273 at Day 29 or Month 3.

Supportive analyses of the primary immunogenicity endpoints at Day 29 and Month 3 will also be performed in the PPSI. These analyses will be based on the ANCOVA model described above and will include pre-booster/baseline SARS-CoV-2 status (negative, positive, or missing) as a factor. The 99% CI for GMR will be used to assess differences between groups at Day 29 and the 96% CI for GMR at Month 3.

6.4.2.2.2. Secondary Analyses

The same ANCOVA model described above will be used for secondary analyses to assess for immune response of mRNA-1273.214 compared to mRNA-1273 booster administered as a 4th dose against other variants at Day 29 or Month 3. The GMT will be estimated by the GLSM from the model and its corresponding 95% CIs will be provided for each group. The GMR for mRNA-1273.214 with respect to mRNA-1273 will be estimated by the ratio of GLSM from the model and the corresponding 95% CIs will be provided. No hypothesis tests will be performed for these objectives.

SRR of the mRNA-1273.214 booster administered as a 4th dose against the B.1.1.529 strain, prototype strain and other variants of concern (VOC) will be analyzed in the PPSI-Neg using the methods as described in [Section 6.4.2.1.2](#). A sensitivity analysis of SRR will be performed in the PPSI by using stratified Miettinen-Nurminen method, with pre-booster positive, negative, and unknown SARS-CoV-2 status as strata.

MMRM as described in [Section 6.4.2.1.2](#). will be used to assess immune response mRNA-1273.214 against both the B.1.1.529, the prototype strain, and other VOC at all measured timepoints after study vaccine administration.

6.4.2.2.3. Exploratory Analyses

Cellular immunity in a subset of participants may be assessed by evaluating the frequency, magnitude, and phenotype of virus-specific T-cell and B-cell responses measured by flow cytometry or other methods, and to perform targeted repertoire analysis of T-cells and B-cells after vaccination.

The same ANCOVA model described above may be used for exploratory analyses to assess for immune response of mRNA-1273.214 compared to mRNA-1273 booster administered as a 4th dose against both the B.1.1.529 and the prototype strain at Day 29, using a 95% CI for GLSM and GMR.

The same ANCOVA model described above will be used for exploratory analyses to assess for immune response of mRNA-1273.214 compared to mRNA-1273 booster administered as a 4th dose against the B.1.1.529 strain, the prototype strain and other variant strains at Month 6 and Month 12 overall and by Phase B subgroup stated in [Section 6.1](#).

Additionally, the SRR will be summarized at Month 6 and Month 12 for each treatment group and by Phase B subgroup with the 95% CI calculated using the Clopper-Pearson method.

Similar analyses will be used to assess for immune response of mRNA-1273.214 compared to mRNA-1273 booster administered against the BA.4/BA.5 variant strains, conducted in the random sample of 200 participants. The exception will be the sensitivity analysis of SRR performed in the PPSI using the stratified Miettinen-Nurminen method, where both SARS-CoV-2 status (positive, negative, and unknown) and age group (≥ 16 to < 65 , and ≥ 65 years) will be included as strata.

6.4.2.3. Sensitivity Analyses

Sensitivity analyses may be performed on the primary immunogenicity endpoints using the Modified PPSI-Neg population and the methods described above.

If there is more than 10% missing immunogenicity data at Day 29 or Month 3, sensitivity analyses to assess the robustness of findings will be performed. The analyses will be performed in the PPSI and missing will be addressed using multiple imputation to impute missing antibody titer data assuming missing at random. The procedure is outlined as follows:

Step 1: Data imputation using Markov Chain Monte Carlo (MCMC) model including treatment group, pre-booster baseline titer, age group, Day 29/Month 3 (if applicable) antibody titer value in the log scale (with a base of 10). Should the data follow a non-monotone missing pattern, partial imputation will be performed first to create a monotone missing data pattern.

Step 2: Estimation using ANCOVA on each imputed dataset in which model includes treatment group as a fixed effect, adjusting for pre-booster baseline titer value and age group. The estimated GMR and standard errors in Log 10 scale will be estimated from each ANCOVA model.

Step 3: Pool the parameter estimates into a single estimate using Rubin's method (1987), back transform the combined estimate back to the original scale.

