Once non-inferiority against B.1.1.529 is demonstrated, superiority of mRNA-1273.529 as compared to mRNA-1273 against B.1.1.529 will be tested (key secondary hypothesis). Specifically, superiority of mRNA-1273.529 as compared to mRNA-1273 will be demonstrated if the lower bound of the 99% CI of the GMR is > 1 (Day 29) or the lower bound of the 96% CI of the GMR is > 1 (Month 3).

Supportive analyses of the primary and key secondary immunogenicity endpoints at Day 29 and Month 3 will also be performed in the PPSI. These analyses will be based on the ANCOVA model described above and will include the pre-booster/baseline SARS-COV-2 status (negative, positive, or missing) as a factor. The 99% CI for GMR will be used to assess differences between groups at Day 29 and the 96% CI for GMR at Month 3.

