PPSI will be used as the analysis population to summarize the immune responses (antibodies of interest) and the above summary statistics including GMT and GMFR will be provided by pre-booster/study baseline SARS-CoV-2 status.

The SRR is measured by an increase of SARS-CoV-2-specific bAb or nAb titer or value (level) from pre-booster below the lower limit of quantification (< LLOQ) to at least 4 x LLOQ, or a 4-fold or greater rise if pre-booster \geq LLOQ.

The SRR will be summarized at all measured time points for each treatment group with the 95% CI calculated using the Clopper-Pearson method. The difference of SRRs at all measured time points for mRNA-1273.529 compared with mRNA-1273 will be provided with 95% CI using Miettinen-Nurminen method. Analysis of the SRR will be performed in the PPSI-Neg. A sensitivity analysis of SRR will be performed in the PPSI by using stratified Miettinen-Nurminen method, with pre-booster positive, negative, and unknown SARS-CoV-2 status as strata.

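### The multiple-imputation sensitivity analysis in the PPSI omits baseline SARS-CoV-2 status, which the plan's own PPSI ANCOVA includes, so the effect of missing titres is not cleanly isolated

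*SAP*

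**What the plan says.** SAP 6.4.2.3 makes the analysis conditional: "If there is more than 10% missing immunogenicity data at Day 29 or Month 3". It then states: "The analyses will be performed in the PPSI and missing will be addressed using multiple imputation". The imputation assumes that titres are missing at random.

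- Step 1 imputes from a "model including treatment group, pre-booster baseline titer, age group, Day 29/Month 3 (if applicable) antibody titer value in the log scale".
- Step 2 fits an ANCOVA to each completed data set; the "model includes treatment group as a fixed effect, adjusting for pre-booster baseline titer value and age group".
- Step 3 pools the estimates.

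SAP 5.4 defines the PPSI without any restriction on infection. SAP 6.4.1 confirms that it contains baseline-seropositive participants, since 40 of the 200 sampled per Part for BA.4/BA.5 testing were seropositive.

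Elsewhere the SAP accounts for status when it analyses the PPSI. The Part 1 supportive ANCOVA (6.4.2.1.1) "will include the pre-booster/baseline SARS-COV-2 status (negative, positive, or missing) as a factor", and the Part 2 version (6.4.2.2.1) "will include pre-booster/baseline SARS-CoV-2 status (negative, positive, or missing) as a factor". The PPSI sensitivity analysis of seroresponse (6.4.2.1.2, repeated for Part 2 in 6.4.2.2.2) is stratified "with pre-booster positive, negative, and unknown SARS-CoV-2 status as strata".

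The primary analysis uses the PPSI-Neg (SAP 5.5), which admits only participants with no evidence of infection at baseline or up to the visit.

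**The concern.** The analysis exists to show whether the primary finding is robust to missing titres. To do that, it should differ from some planned analysis only in how missing titres are handled. It mixes baseline-negative and baseline-positive participants in one model without the factor that the plan uses elsewhere for that mixture, and it gives no reason. Missing at random, conditional on the listed variables, is also harder to defend when an already collected baseline factor that may predict both titre and missingness is left out. If the imputed GMR moved away from the primary or the supportive GMR, part of the shift could come from the change of population or from the dropped factor.

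**Working it through.** **1. Specifications side by side.** I take the analysis to concern the 4th-dose group, as the primary tests do; SAP 6.4.2.3 does not restate this.

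| Analysis | Set | Adjusted for, besides arm | Missing titres |
|---|---|---|---|
| Primary ANCOVA | PPSI-Neg | age group, last vaccine type, baseline titre | observed only |
| Supportive ANCOVA | PPSI | the same plus baseline status | observed only |
| Multiple imputation | PPSI | age group, baseline titre | imputed |

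Last vaccine type is mRNA for every eligible 4th-dose participant (Protocol 5.1, criterion 7), so losing it changes nothing there. Baseline status is constant in the PPSI-Neg. That leaves:

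- imputation against primary: the set and the missing-data handling change;
- imputation against supportive: baseline status and the missing-data handling change.

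The optional Modified PPSI-Neg sensitivity analysis does not help as planned, because no imputation is planned in that set. The reference in 6.4.2.3 to methods described above belongs to that optional analysis and does not bring status into Steps 1 and 2.

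**2. Size.** The plan gives no figure to reproduce, and its titre SD and assumed GMRs are redacted. Every input here is therefore an assumption: true GMR 10^0.2 = 1.585, residual SD 0.35 log10, 400 per arm, 10–30% baseline-positive, and a status effect given baseline titre between −0.2 and +0.2 log10. Steps 1–3 were simulated with and without status (300 replicates, 20 imputations). The simulation error of each mean is about 0.0265/√300 = 0.0015 log10, or roughly 0.4%. Comparisons within a row use the same data sets, so they are tighter.

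*Missingness 10% in negatives and 30% in positives, the same in both arms.* The two imputation versions differ by at most about 0.2% (largest gap 1.5929 against 1.5963). Omitting status raises the standard error by 0 to 3% (largest 0.0278/0.0271 = 1.026).

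*Missingness 10% throughout, except 40% among positives in the test arm.*

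| Positive share | Status effect | Full data | Without status | Shift | With status |
|---|---|---|---|---|---|
| 10% | +0.2 | 1.5908 | 1.5739 | −1.1% | 1.5934 |
| 20% | +0.2 | 1.5850 | 1.5510 | −2.1% | 1.5823 |
| 30% | +0.2 | 1.5840 | 1.5404 | −2.8% | 1.5831 |
| 10% | −0.2 | 1.5881 | 1.6075 | +1.2% | 1.5889 |
| 20% | −0.2 | 1.5855 | 1.6190 | +2.1% | 1.5866 |
| 30% | −0.2 | 1.5888 | 1.6347 | +2.9% | 1.5916 |

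With a status effect of +0.1 the shifts are about 0.7–1.2%.

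Hand check of the 20%, +0.2 row, ignoring baseline titre. The observed positive share in the test arm is 0.2×0.6/(0.2×0.6 + 0.8×0.9) = 0.12/0.84 = 0.143, against 0.200 in the control arm. The bias is about 0.2×(0.143 − 0.200) = −0.0114 log10, a factor of 10^−0.0114 = 0.974, or −2.6%. The simulated −2.1% is somewhat smaller, as expected if baseline titre picks up part of the status difference.

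**3. Change of set.** Suppose the GMR is lower by 0.1 log10 in positives. Full-data PPSI should then give 10^(0.2 − 0.1p), that is 1.549, 1.514 and 1.479 for p = 10%, 20% and 30%; the simulation gave 1.549, 1.513 and 1.488. Imputation in the PPSI gave 1.556, 1.524 and 1.507, against 1.583, 1.582 and 1.599 in observed baseline-negative participants, who stood in for the PPSI-Neg. That gap comes mainly from the population. Adding status as a main effect does not remove it (1.557, 1.523, 1.506).

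**The case against.** The choice of the PPSI is defensible. The PPSI-Neg requires negative RT-PCR and serology on the day of the analysis visit (SAP 5.5), so someone who misses the visit generally cannot be classified into it. The baseline titre is in both models and carries part of the information on prior infection. The analysis runs only above 10% missing and decides no hypothesis. Nothing in the documents suggests that missingness would differ by arm and status together in an observer-blind, single-dose trial. All of this stands, and it limits the size of the point.

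A reader might also infer three stronger things that the documents do not support.

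- That population, covariates and missing-data handling all change at once against the primary analysis. Effectively only two of them do: status is constant in the PPSI-Neg and vaccine type is constant in the 4th-dose group.
- That a discrepancy could not be attributed at all. The observed-data PPSI ANCOVA, the subgroup analyses by pre-booster status and by status at the visit (SAP 6.1), and the optional Modified PPSI-Neg analysis allow partial attribution.
- That status is a strong predictor once baseline titre is in the model. No document gives such an effect, and the 40 in 200 of the BA.4/BA.5 sample is a sampling quota, not a prevalence.

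None of this explains why this PPSI model alone drops the factor.

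**Conclusion.** The inconsistency is real and minor. No firmly planned comparison differs from the imputation analysis only in its treatment of missing titres. The clearest mismatch is with the supportive PPSI ANCOVA, where one dropped covariate stands in the way; against the primary analysis, the change of set does. The consequence for the GMR is about 1–3% if missingness among positives is 10% in one arm and 40% in the other with a residual status effect of 0.2 log10 in either direction. There is no material bias if missingness is balanced, and the standard error is 0–3% larger. These sizes rest wholly on assumed inputs. They are small against a margin of 1.5 and could matter only to a reading close to the superiority boundary. The primary tests are unaffected.

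**What to change.** In SAP 6.4.2.3, add baseline SARS-CoV-2 status (negative, positive, missing) to Step 1 and Step 2, and state that the result is to be compared with the observed-data supportive PPSI ANCOVA. In the 4th-dose group those two analyses then differ only in the handling of missing titres. The missing level is already defined, so no new missing covariate arises. The cost is one term in each of two models and one sentence.

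Optionally, repeat the imputation in the Modified PPSI-Neg, which is defined by baseline tests only (SAP 5.6) and so can hold participants who missed the visit. This helps only if the observed-data Modified PPSI-Neg ANCOVA, now optional, is made firm as its comparator. It would give one comparison among baseline-negative participants that changes only the missing-data handling, at the cost of one further table.

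I would not add a term for infection after baseline. For the participants whose titres are imputed, status at the visit would often be unknown, because those tests belong to the missed visit.

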6.5. Efficacy Analysis

Number and incidence rates of symptomatic COVID-19 disease, asymptomatic SARS-CoV-2 infection, as well as COVID-19 regardless of symptoms will be provided for each study arm. Vaccine efficacy and the respective 95% CI will also be estimated. Efficacy analyses will be performed using the mITT and PPSE analysis populations.

Pre-booster SARS-CoV-2 status is determined by using virologic and serologic evidence of SARS-CoV-2 infection on or before Day 1 (pre-booster).

Participants with baseline positive or missing SARS-CoV-2 status will be excluded from the PPSE and mITT Set.

In this study, the serology test results based on bAb specific to SARS-CoV-2 nucleocapsid, and the RT-PCR test results will be summarized by visit.

The primary analysis population to assess incidence of symptomatic SARS-CoV-2 infection (COVID-19), asymptomatic SARS-CoV-2 infection, and SARS-CoV-2 infection is PPSE, unless otherwise specified. mITT may be used for supportive analyses. All results will be summarized by treatment group.

Exploratory analyses for the efficacy endpoints may be performed by Phase B subgroup stated in [Section 6.1](#).

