All analyses and data summaries/displays for disposition, baseline demographics and characteristics will be provided by treatment group unless otherwise specified. All analyses and data summaries/display for efficacy will be provided by treatment group using the appropriate analysis population unless otherwise specified.

Subgroup Analysis

Immunogenicity will be assessed in the following subgroups:

- Age (≥ 16 to < 65 , and ≥ 65 years)
- Sex (female, male)
- SARS-CoV-2 status (negative, positive) at the day of analysis visit (e.g., for Day 29, subgroup analyses will be performed based on SARS-CoV-2 status up to Day 29 visit)
- Pre-booster SARS-CoV-2 status (negative, positive)
- Race and ethnicity group (White, Mixed or Multiple ethnic groups, Asian or Asian British, etc.)
- In addition, Phase B in each study Part (analyses may be performed in two or four subsets):
 - Two subsets
 - Subset of participants in the 4th dose group who received an additional booster outside of the study.
 - Subset of participants in the 4th dose group who did not receive an additional booster outside of the study.
 - Four subsets

- Subset of participants in the 4th dose group who were unblinded to study IP and received an additional booster outside of the study.
- Subset of participants in the 4th dose group who were unblinded to study IP and did not receive an additional booster outside of the study.
- Subset of participants in the 4th dose group who remained blinded to study IP and received an additional booster outside of the study.
- Subset of participants in the 4th dose group who remained blinded to study IP and did not receive an additional booster outside of the study.

Safety and efficacy may be assessed for the same subgroups.

Analyses Approach

All analyses and data summaries/displays will be provided by study arm (mRNA-1273.529 and mRNA-1273 for Part 1, and mRNA-1273.214 and mRNA-1273 for Part 2) and by treatment subgroups (IP administrated as 3rd or 4th dose) using the appropriate analysis population, unless otherwise specified. Data summaries for participants disposition, baseline demographics, and safety data may also be provided by treatment group.

All analyses will be conducted using SAS Version 9.4 or higher unless otherwise specified.

Immunogenicity Measures

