6.5.1. Endpoint Definition/Derivation

6.5.1.1. Derivation of SARS-CoV-2 Infection

SARS-CoV-2 infection will be defined in participants with negative SARS-CoV-2 status pre-booster by either:

- bAb levels against SARS-CoV-2 nucleocapsid protein negative (as measured by *Roche Elecsys*) at Day 1 that becomes positive (as measured by *Roche Elecsys*) post-baseline, OR
- Positive RT-PCR post-baseline.

The date of documented infection will be the earlier of:

- Date of positive post-baseline RT-PCR result, or
- Date of positive serology test result based on bAb specific to SARS-CoV-2 nucleocapsid

The time to the first SARS-CoV-2 infection will be calculated as:

Time to the 1st SARS-CoV-2 infection = Date of the 1st documented infection – Date of randomization + 1.

Cases will be counted starting 14 days after the randomization, i.e., date of documented infection – date of randomization \geq 14.

The incidence of SARS-CoV-2 infection counted starting 14 days after randomization will be summarized by treatment group.

Supportive analyses will summarize incidence of SARS-CoV-2 infection in which a case is counted after randomization, i.e., date of documented infection – date of randomization \geq 0.

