6.5.2. Analysis Method

The number and percentage of participants who had each type of event (i.e., an asymptomatic or a symptomatic SARS-CoV-2 infection) will be summarized in the PPSE.

As per Phase B, participants are allowed to receive an additional booster outside of the study. Participants who received this additional booster may be censored in the efficacy analyses at the time of booster, as outlined below.

The incidence rate of each type of event will be calculated as the number of cases divided by the total person-time. Person-time is defined as the total time from randomization date to the date of event, last date of study participation, censoring time, date of additional booster outside of the study or efficacy data cutoff date, whichever is earlier.

The 95% CI of the incidence rate will be calculated using the exact method (Poisson distribution) and adjusted by person-time.

Vaccine efficacy and the respective 95% CI will also be estimated.

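### Efficacy by Phase B subgroup groups participants by a later outside booster but ends person-time at that booster, so the boosted subgroup's rate contains no post-booster time and its bias has no fixed direction

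*SAP*

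**What the plan says.** SAP 6.1 (Subgroup Analysis) defines Phase B subsets by what a participant did after randomization, for example "Subset of participants in the 4th dose group who received an additional booster outside of the study", set against those who did not. A four-subset version also splits by unblinded or still blinded. The section adds: "Safety and efficacy may be assessed for the same subgroups". SAP 6.5 repeats the permission for efficacy: "Exploratory analyses for the efficacy endpoints may be performed by Phase B subgroup stated in" Section 6.1.

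SAP 6.5.2 gives the only incidence-rate method. "Person-time is defined as the total time from randomization date to the date of event", or to one of several other stopping points, among them "censoring time, date of additional booster outside of the study or efficacy data cutoff date, whichever is earlier". The preceding paragraph is only permissive: "Participants who received this additional booster may be censored in the efficacy analyses at the time of booster, as outlined below". In the main analysis, "Cases will be counted starting 14 days after the randomization" (SAP 6.5.1.1, with the same rule for symptomatic cases in 6.5.1.3). Counting from randomization itself is a supportive analysis.

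SAP 4.6 opens optional unblinding after the Month 3 visit in Part 2 and after the Month 6 visit in Part 1. No separate time origin, and no time-varying treatment of the booster, is given for the Phase B efficacy subgroups.

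**The concern.** Membership of the boosted subgroup is known only once the booster has been given, yet all the person-time credited to that subgroup lies before it. The resulting rate describes the months leading up to the event that defines the group. It says nothing about what happened afterwards, which is the period a reader of a Phase B table would expect to see.

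The subgroups also condition on something infection may influence. If infection makes people defer or skip a booster, cases move into the unboosted subgroup. If incidence changes over the year, the two subgroups are compared over different stretches of calendar time. If cases after the booster are kept while person-time stops there, numerator and denominator no longer match. Each route can create a difference between subgroups when neither the booster nor the study vaccine has any effect. Because 6.5 summarizes results by treatment group and 6.5.2 estimates vaccine efficacy, arm comparisons inside these post-randomization groups could be reported too.

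**Working it through.** The documents state no infection rate, booster uptake or efficacy power, so there is no plan figure to reproduce.

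**Inputs from the documents.** Person-time starts at randomization and stops at the booster (SAP 6.5.2). Cases count from 14 days after randomization (SAP 6.5.1.1, 6.5.1.3). Phase B opens after Day 85 in Part 2 and Day 179 in Part 1 (SAP 4.6, Appendix E). Last visit is Day 359.

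**Assumptions, none from the documents.** Infection hazard 0.2, 0.5 or 1.0 per person-year. Half of participants intend an outside booster, at a date spread evenly over the 60 days after Phase B opens, so the mean booster day is 85 + 30 = 115 (Part 2) or 179 + 30 = 209 (Part 1).

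**Step 1: infection does not affect uptake, constant hazard, post-booster cases dropped.** At low hazard each subgroup's rate is h × (1 − 14 / mean stopping day), because the first 14 days add time but no countable cases.
- Part 2: (1 − 14/115) / (1 − 14/359) = 0.878 / 0.961 = 0.91.
- Part 1: (1 − 14/209) / (1 − 14/359) = 0.933 / 0.961 = 0.97.

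Simulation (2 million participants per scenario) gives 0.91–0.92 and 0.97–0.98.

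**Step 2: prior infection halves uptake.** The boosted rate is multiplied by about 0.5. In the unboosted subgroup, infections before the planned booster have weight 0.75 and everything else 0.5.
- Part 2: the unboosted rate is multiplied by (0.75 × 101 + 0.5 × 244) / (0.5 × 345) = 1.15, where 101 = 115 − 14, 244 = 359 − 115 and 345 = 359 − 14. The ratio is 0.91 × 0.5 / 1.15 = 0.40.

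Simulation over both Parts and all hazards gives 0.39–0.46. If prior infection stops uptake altogether, the ratio is 0.

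**Step 3: incidence changes after Phase B opens, uptake unaffected.** Hazard doubled: 0.66–0.80. Hazard halved: 1.16–1.29.

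**Step 4: post-booster cases kept, person-time still stopped, uptake unaffected.** At low hazard both subgroups count cases over the same days, so the ratio tends to 359/115 = 3.1 in Part 2 and 359/209 = 1.7 in Part 1. Simulation gives 2.3–2.9 and 1.4–1.7, falling as the hazard rises. If prior infection stops uptake, it gives 1.3–1.6 in Part 2 and 0.44–0.47 in Part 1.

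**Step 5: can the rule detect a booster effect?** With post-booster cases dropped, a true booster effect of 0% or 50% gives the same ratio: 0.91 and 0.91 with uptake unaffected, 0.41 and 0.41 with uptake halved (Part 2, hazard 0.5).

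**Step 6: arm comparison inside subgroups.** Hazard 0.5 per year in both arms (true ratio 1.0), booster between Days 90 and 270. Uptake of 40% if uninfected and 30% if infected in one arm, against 70% and 35% in the other, gives arm ratios of about 1.45 (boosted) and 0.72 (unboosted). With 60% and 40% in both arms the ratio is 1.00 in each subgroup. It is also 1.00 when uptake differs by arm (40% against 70%) but does not depend on infection.

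**Step 7: the remedy.** Person-time from the Phase B visit in the uninfected, split at the booster, gives 0.99–1.01 for a true effect of 0% and 0.50 for 50%, in every uptake scenario and both Parts under constant hazard.

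**The case against.** The strongest reply is that this is an under-specified optional analysis, not a prescribed wrong one. Section 6.5 uses permissive wording and names no method for the Phase B subgroups. It plans no boosted-to-unboosted ratio and summarizes by treatment group. Censoring at the booster is itself optional. With uptake unrelated to infection and constant incidence the distortion is small (Step 1), and the four-subset option isolates blinded participants, whose uptake cannot depend on knowing their arm.

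Much of that stands. A reader might infer that the boosted rate must come out artificially low. It need not: that requires infection to deter or delay boosting, or incidence to rise later, and Steps 3 and 4 show the reverse. A reader might call this immortal time. That is too strong, since someone infected before the booster can still be boosted and still counts as a case in the boosted subgroup. Nor do the documents say a booster is possible only after Month 3 or Month 6: those visits open optional unblinding, and outside COVID-19 vaccines are recorded at any time during the study. Arm comparisons are not biased by this route unless the link between infection and uptake differs by arm, and no passage says that it does.

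What does not stand is the claim that only detail is missing. The one person-time rule in the SAP, applied to the subgroups that the SAP names, leaves no post-booster time in the boosted denominator. The mismatch between optional censoring and an unconditional stop to person-time is in the text of 6.5.2.

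**Conclusion.** The point holds in this form: the Phase B efficacy subgroups are defined by a post-randomization event, and the stated person-time rule ends at that event. The boosted rate therefore carries no information about post-booster efficacy. Its bias relative to the unboosted rate has no direction that the SAP fixes. With no true booster effect, the illustrations run from 0 to 0.98 when post-booster cases are dropped and incidence is constant, reach 1.29 when incidence falls, and reach 2.9 when post-booster cases are kept.

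All of these magnitudes rest on assumed hazards, uptake and booster timing. The structural conclusion does not. Severity is minor to moderate: the analysis is optional and exploratory, and no primary or secondary conclusion depends on it.

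**What to change.** In SAP 6.5 and 6.5.2, for any efficacy summary by Phase B status:

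- Start person-time at the completed Month 3 visit (Part 2) or Month 6 visit (Part 1), among participants still uninfected, not yet boosted outside the study, and in follow-up.
- Split person-time at the outside-booster date as a time-varying state, and count each case in the state on its date.
- State one rule so that cases and person-time stop or continue together after the booster.
- Say how infections found only by serology are handled when the interval between tests spans the booster. They are dated by the positive test (SAP 6.5.1.1), and after Month 3 surveillance blood is drawn only at Days 179 and 359. One option is to use RT-PCR-dated cases, with serology cases as a sensitivity analysis.
- Say whether boosted participants remain in the PPSE, since protocol 6.5.3 lets an outside COVID-19 vaccine affect per-protocol evaluability.
- Report time before Phase B by randomized arm only, and label Phase B rates non-randomized and descriptive. The remedy was checked under constant hazard only, so changing incidence remains a caveat.

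The cost is SAP wording and routine programming. Outside COVID-19 vaccinations are already recorded to end of study (protocol 6.5.2; SAP Appendix E). The downside is fewer person-days per cell than counting from randomization.
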